Sample Size: Sample size calculation was based on prior research and our primary focus which is on physical activity and function 12,14,15,33,106. For primary patient level outcomes, function based on the Barthel Index resulted in a Cohen's d=.24, for physical activity the Cohen's d=.37, and for participation in function focused care by patients Cohen's d=.31. The impact on tethering, a secondary outcome, was noted to have a Cohen's d=.61. Given a two-tailed alpha of .05, an estimated intra-class correlation coefficient (ICC) between clusters (hospitals) of .02, a correlation coefficient between repeated measures of .60, and assuming even dispersion of means, a total sample of 360 patients will provide sufficient power (>.80) to detect a small effect size (d=.24)¹³⁸ in primary patient level outcomes. Our prior research showed an attrition rate of 5-40% over a 12- month period. Therefore, we anticipate that a total of 600 patients from 12 hospitals (50 patients per hospital) will be sufficient to demonstrate outcomes. With regard to hospital level outcomes, our prior work resulted in effect sizes of 0.9 for environment and policy changes 15,33,106,139. With the proposed sample size of 12 hospitals the statistical power for these measures will be adequate (.90 for both outcomes based on our analysis plan).

Settings: Hospitals will be invited to participate if they: (a) have at least one unit dedicated to general medical patients; (b) identify two registered nurses (RN) to be champions (one for day and one for evening shifts); (c) enable staff to access email and websites via a phone, tablet or

computer; and (d) do not have a geriatric program (e.g., Acute Care for Elders, Hospital for Elder Life Program/ HELP) on the study units. We will implement FFC-AC-EIT in 6 hospitals (on the medical unit) and EO in 6 hospitals (on the medical unit) across Maryland and Pennsylvania. (See support letters and Facilities and Resources section).

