model to adjust for their influences. Random effects will include hospitals and patients. The hypotheses will be tested by evaluating the interaction term for each outcome variable. For each hypothesis, exploratory analyses will be performed to assess model assumptions. Post-analysis diagnostic measures (e.g., residuals) will be explored to assess model fit. All tests will use a 5% significance level. The use of LMM will provide flexibility with regard to assumptions related to the covariance structure of the residuals and the presence of missing data for the repeated measures¹⁷¹. As secondary analyses, we will also consider three-way interactive effects among demographic variables of interest (e.g., sex, age), and treatment condition, and time to identify moderators of the treatment effects. All of the Research Nurse Facilitators are women so we do not anticipate an effect of sex on outcomes. Generalized estimating equation (GEE) models will be used to compare changes in hospital level measures (i.e., environments, policies) (Hypothesis 3) from baseline to 6,12, and 18 months as GEE is more robust than LMMs when the sample size is relatively small (n=12)¹⁷².

Missing data. In prior research we had a 5-40% rate of attrition at the patient level and 0% at the hospital level^{12,33}. If there is significant dropout, we will identify baseline characteristics that differ between persons or hospitals that drop out. Maximum likelihood methods will be used for primary analyses, which address non-informative dropout [missing at random (MAR)]. If "informative" dropout is present, we will consider sensitivity analyses that add these relevant baseline covariates to make the MAR assumption more plausible¹⁷³.

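### The sensitivity analysis for informative dropout still assumes missing at random, so it cannot show whether the 6- and 12-month results depend on that assumption

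*Combined protocol and SAP*

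**What the plan says.** The Missing data paragraph (end of Data Analysis) opens with experience: "In prior research we had a 5-40% rate of attrition at the patient level", and none at hospital level. If dropout is substantial, baseline characteristics related to it will be identified. The primary analyses use maximum likelihood, which the plan itself ties to non-informative dropout, that is, MAR. For informative dropout it adds: "we will consider sensitivity analyses that add these relevant baseline covariates to make the MAR assumption more plausible".

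No other analysis of departures from MAR appears: no delta adjustment, pattern-mixture or selection model, reference-based imputation or tipping point. The documents do not mention death as a reason for missing outcomes.

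Three other places bear on this:
- Sample Size gives the same attrition range over 12 months, and for the planning effect "function based on the Barthel Index resulted in a Cohen's d=.24".
- Sample and Setting places function and physical activity after discharge under Hypothesis 2, at 1, 6 and 12 months.
- Data Analysis fits a linear mixed model to up to five occasions from admission onward, with hospital and patient as random effects and adjustment for sex, comorbidity and cognition.

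**The concern.** The plan contrasts informative dropout with MAR, then answers it with a model that assumes MAR. Dropout that is informative in this sense depends on outcomes nobody recorded, even after conditioning on everything that was recorded. More baseline covariates narrow that gap only where they explain it, and the fitted model gives no sign of what remains.

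Three features weaken the safeguard further:
- The analysis is only to be considered.
- Its trigger, that informative dropout is present, cannot be established from observed data.
- Some likely covariates (sex, comorbidity, cognition) are already meant for the primary model, so the two fits may differ little.

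At stake is the reading of the later Hypothesis 2 results. Either a benefit or a null finding at 12 months could rest on MAR, and the planned analysis would not reveal it.

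**Working it through.** **1. The plan's own figure.** Sample Size needs 360 evaluable patients and enrols 600. The step between is not shown, but 360 / (1 − 0.40) = 600 exactly. Enrolment therefore matches the top of the attrition range.

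**2. What each model assumes.** The primary model assumes MAR given earlier outcomes, arm, time and the chosen covariates. The sensitivity model assumes MAR given the same set plus more baseline covariates. In both, missing values follow the same distribution as observed values with the same history. Agreement between the two shows insensitivity to the covariate set, not to MAR.

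**3. Size of a departure.** Let π be the fraction missing in an arm at a time point, and let δ be how much worse, in SD, the missing patients do than MAR predicts. Then:
- true arm mean = MAR arm mean − π × δ
- change in the contrast (FFC-AC-EIT minus EO) = −(π_FFC × δ_FFC − π_EO × δ_EO)

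The 5% and 40% rows use the ends of the documents' range; 20% is an intermediate assumption. All values of δ are assumptions. The last column takes the MAR estimate to be the planning value of 0.24.

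| π | shift at δ = 0.2, one arm | shift at δ = 0.6, one arm | δ that brings 0.24 to zero (0.24/π) |
|---|---|---|---|
| 0.05 | 0.01 | 0.03 | 4.8 |
| 0.20 | 0.04 | 0.12 | 1.2 |
| 0.40 | 0.08 | 0.24 | 0.6 |

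At 40% missing, δ = 0.2 removes 0.08/0.24 = 33% of the planning effect for function. For physical activity (planning d = .37) the zero point is 0.37/0.40 = 0.93 SD.

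**4. Other patterns.**
- Equal attrition and equal δ in both arms: shift of 0.
- Attrition of 40% in FFC-AC-EIT and 30% in EO (assumed), δ = 0.6 in both: (0.40 − 0.30) × 0.6 = 0.06 SD, or 25% of 0.24.
- Departure in EO only: the same sizes in the opposite direction, so MAR could also hide a benefit.

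**5. How large 0.6 SD is.** The plan assumes "a correlation coefficient between repeated measures of .60". Given baseline alone, the residual SD is √(1 − 0.6²) = 0.8, so δ = 0.6 is 0.6/0.8 = 0.75 residual SD. That is a substantial departure.

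**6. Significance.** At 40% missing there are 300 × 0.6 = 180 patients per arm and 50 × 0.6 = 30 per hospital. With the plan's ICC of .02, the design effect is 1 + 29 × 0.02 = 1.58. With a baseline-adjusted variance of 1 − 0.6² = 0.64, SE = √(2/180 × 0.64 × 1.58) = 0.106. An estimate of 0.24 then has z = 2.26. Holding the SE fixed, significance is lost at δ = (0.24 − 1.96 × 0.106)/0.40 ≈ 0.08 SD. With a change-score variance of 2(1 − 0.6) = 0.80, SE = 0.119 and δ ≈ 0.02 SD. The plan does not say which variance its power rests on, so these values are indicative only.

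**The case against.** The strongest defence has four parts.

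- **Covariates can help.** Dropout that is not MAR without a covariate can become MAR once a predictor of both dropout and outcome is added. The plan claims only to make MAR more plausible. This stands: the remedy is incomplete, not useless.
- **The primary model already protects.** It uses each patient's earlier outcomes, so decline recorded before a patient leaves is conditioned on. Only decline beyond what the recorded trajectory predicts is at issue. Eligibility also requires a contactable family member or caregiver, and post-discharge activity, falls and admissions come from informants. This stands too. A reader might infer that frail patients will be the ones lost; that is reasonable to suspect, but the documents do not show it.
- **40% is an upper bound.** It is the top of a 12-month range, and the documents give no attrition at 1 or 6 months. A reader might apply 40% to every visit; the text does not support that. The discharge outcomes of Hypothesis 1 are largely outside the concern.
- **The large shift is constructed.** A departure of 0.6 SD is simply 0.24/0.40, placed wholly in one arm. Nothing in the documents makes it likely, and symmetric departures cancel when attrition is equal.

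These points limit the size and reach of the concern. None of them supplies an analysis that departs from MAR.

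**Conclusion.** The concern holds in limited form. Followed exactly, the plan has no analysis that could show whether a later Hypothesis 2 result depends on MAR. The exposure is greatest for function and physical activity at 6 and 12 months, may be large if attrition approaches the 40% that enrolment matches, and is minor near 5% (0.03 SD at most for departures up to 0.6 SD). The sizes rest on assumed departures in one arm and on an estimate equal to the planning value.

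Two stronger readings should be resisted. One is that the 12-month results will be biased: the documents give no evidence on the direction or size of any departure, or on whether it differs by arm. The other is that a departure below 0.1 SD overturns the trial. That figure mainly reflects how little an estimate of 0.24 exceeds the significance threshold at 40% missing (z = 2.26 under one variance assumption), and it changes with a variance model that the plan does not state.

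**What to change.** Keep maximum likelihood under MAR as the primary analysis, and keep the covariate-enriched model as a supporting one. Add to the SAP:

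1. A prespecified delta-adjusted (pattern-mixture) multiple-imputation analysis for function and physical activity after discharge, with 6 and 12 months of main interest and hospital in the imputation model.
2. A commitment to run it whatever any comparison of dropouts shows, in place of wording that it will be considered.
3. Shifts of imputed values in FFC-AC-EIT only, in EO only and in both arms, so that positive and null findings are both probed.
4. A range of shifts wide enough to find where the conclusion changes, with that point reported. Since the zero point is the estimate divided by the missing fraction, a fixed ceiling of 0.6 SD would miss it at 20% attrition (1.2 SD). If only an implausibly large shift changes the conclusion, that is itself the reassurance sought.
5. A statement of how outcomes after death are handled, separately from loss to follow-up, so that function is not imputed after death without a defined meaning.

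The cost is SAP wording and modest programming. No new data are needed.
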